2.4.4.2 Analyses of secondary efficacy endpoints

For continuous secondary efficacy parameters (see [Section 2.1.3](#)) with missing data at baseline, missing data will be imputed using MI under the missing at random (MAR) assumption. Missing data at baseline will be imputed using regression method that includes randomization stratum of Screening HbA1c ($\leq 8.5\%$, $> 8.5\%$), randomization stratum of Screening SBP (< 130 , ≥ 130 mmHg), and baseline value in the imputation model.

Each continuous secondary efficacy endpoint (Section 2.1.3) will be analyzed using a similar ANCOVA model including the measurements at baseline and endpoint (observed or imputed).

The missing data at endpoint will be imputed by the retrieved dropouts if there are at least 5 patients in each study treatment group who discontinued but have the endpoint. Otherwise, the washout imputation method will be used. After the imputation, each of the complete datasets will be analyzed by an ANCOVA model.

The ANCOVA model will include treatment groups (sotagliflozin 400 mg, sotagliflozin 200 mg, glimepiride, and placebo), randomization stratum of HbA1c ($\leq 8.5\%$, $> 8.5\%$), randomization stratum of SBP (< 130 mmHg, ≥ 130 mmHg), and country as fixed effects, and the corresponding baseline secondary endpoint value as a covariate. For the analysis of SBP in patients with baseline SBP ≥ 130 mmHg, the randomization stratum of SBP will not be included. Results from each complete dataset will be combined using Rubin's formula to provide the adjusted mean change from Baseline to Week 52 (or Week 12 for SBP) for each treatment group, as well as the between-group differences and the 95% CIs for the differences.

For all continuous secondary endpoints, summary statistics at scheduled visits will be provided for each treatment group. The summary will include the number of observations, mean, SD, SE, minimum, median, and maximum. Graphical presentations will also be used to examine trends over time using mean values (\pm SE) and mean changes from Baseline (\pm SE) at each of the scheduled visits. In addition, SBP will be summarized descriptively at each visit for those with baseline SBP ≥ 130 mmHg. Same analyses will also be described for patients with baseline SBP ≥ 140 mmHg.

The categorical secondary efficacy variables of HbA1c $< 6.5\%$, $< 7\%$ at Week 52 will be analyzed respectively using a Cochran-Mantel-Haenszel (CMH) method stratified by randomization stratum of HbA1c ($\leq 8.5\%$, $> 8.5\%$), and randomization stratum of SBP (< 130 mmHg, ≥ 130 mmHg). The proportion in each treatment group will be provided, as well as the difference of proportions between sotagliflozin 400 mg and placebo with associated 2-sided 95% CI. For HbA1c responders at Week 52 ($< 6.5\%$, $< 7\%$ respectively), all values at Week 52 will be used to determine whether a patient is a responder or not, even if they are measured after IMP discontinuation or rescue medication use. Patients who have no HbA1c measurement at Week 26 will be treated as non-responders. Summary tables and graphs will also be provided by treatment group at scheduled visits. For between-group comparison, a sensitivity analysis will be performed respectively for HbA1c $< 6.5\%$ responder analysis by excluding patients whose HbA1c values at baseline are $< 6.5\%$, and for HbA1c $< 7\%$ responder analysis by excluding patients whose HbA1c values at baseline are $< 7\%$ using the same CMH test mentioned above. Similarly, by-visit summary may also be provided excluding those patients.

The categorical secondary endpoint, the proportion of patients with at least one documented symptomatic hypoglycemic event (≤ 3.9 mmol/L [≤ 70 mg/dL]) during the 52-week Treatment Period, will be analyzed respectively using a Cochran-Mantel-Haenszel (CMH) method stratified by randomization stratum of Screening HbA1c ($\leq 8.5\%$, $> 8.5\%$) and randomization stratum of Screening SBP (< 130 mmHg, ≥ 130 mmHg). The proportion in each treatment group will be provided, as well as the difference of proportions between sotagliflozin 400 mg group and glimepiride group with its associated 2-sided 95% CI. Summary tables and graphs will also be provided by treatment group at scheduled visits.

Sensitivity analyses

Tipping-point analysis similar to that is described in [Section 2.4.4.1](#) will be performed to evaluate the robustness of the treatment effect on HbA1c data for the following comparisons, using the same MI method and similar ANCOVA model for the primary endpoint analysis:

- Superiority comparison of sotagliflozin 400 mg and placebo on change from Baseline to Week 26.
- Superiority comparison of sotagliflozin 200 mg and placebo on change from Baseline to Week 26.
- Non-inferiority comparison of sotagliflozin 200 mg and glimepiride on change from Baseline to Week 52.
- Superiority comparison of sotagliflozin 400 mg and glimepiride on change from Baseline to Week 52.

Missing data will be imputed at Week 26 or Week 52 as appropriate. The sotagliflozin groups will be penalized incrementally by a penalty, and repeated until the upper bound of the 2-sided 95% CI is $\geq 0.3\%$ for the non-inferiority comparison or until the p-value for treatment effect between the two treatment groups is >0.05 for the superiority comparison, respectively.

The tipping-point analysis will be performed only if the respective secondary endpoint comparison is statistically significant at a two-sided $\alpha = 0.05$.

A sensitivity analysis will also be conducted with the treatment completers (ie, all patients who complete the 26-week double-blind treatment period and do not start rescue therapy) for noninferiority of sotagliflozin 400 mg versus glimepiride on HbA1c reduction using the same ANCOVA model described in [Section 2.4.4.1](#). The washout imputation method will be used, where missing endpoint data in all treatment groups are imputed from a model estimated from patients in the placebo group who have the endpoint data available. The imputation model will include the randomization strata and the corresponding baseline value. Missing data will be imputed using the regression method.

Assessment of treatment effect by subgroup

Similar to that is described in [Section 2.4.4.1](#), the treatment effects for the following treatment group comparisons across subgroups will be estimated for the change from Baseline in HbA1c in the ITT population, and using the same MI method for the primary endpoint analysis:

- Sotagliflozin 400 mg group vs. placebo group at Week 26.
- Sotagliflozin 200 mg group vs. placebo group at Week 26.
- Sotagliflozin 200 mg group vs. glimepiride group at Week 52.

The ANCOVA model will include treatment groups (sotagliflozin 400 mg, sotagliflozin 200 mg, glimepiride, and placebo groups), randomization stratum of Screening HbA1c ($\leq 8.5\%$, $>8.5\%$), randomization stratum of Screening SBP (<130 mmHg, ≥ 130 mmHg), subgroup factor, treatment-by-subgroup factor, and country as fixed factors and using baseline HbA1c value as a

covariate. The adjusted estimates of treatment mean differences with SE and 95% CIs will be provided as appropriate across the subgroups. A graphical presentation of the results (ie, forest plot) will also be provided.

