Abbreviations: AE = adverse event; AESI = adverse event of special interest; BP = blood pressure; ECG = electrocardiogram; eGFR = estimated glomerular filtration rate; EOSI = events of special interest; EOT = end of treatment; EW = early withdrawal; FPG = fasting plasma glucose; FSH = follicle-stimulating hormone; HbA1c = hemoglobin A1c; IMP = investigational medicinal product; IRT = Interactive Response Technology; NIMP = non-investigational medicinal product; PRO = patient-reported outcome; PQAT = Patient Qualitative Assessment of Treatment; SAE = serious adverse event; SMBG = self-monitoring blood glucose; UTI = urinary tract infection; WOCBP = women of childbearing potential

- a All visits' dates will be scheduled based on the date of randomization within visit window allowed as per flowchart. If a patient discontinues treatment with investigational medicinal product (IMP) during the Treatment Period, the patient will have a visit as soon as possible to complete the assessments normally planned for the last dosing day with the IMP [End of Treatment/Early Withdrawal (EOT/EW) Visit], and a Follow-up Visit 2 weeks after the last dose of IMP. In addition, every effort will be made to have the patients return to the site at the time corresponding to their scheduled visits, particularly the Week 26 and Week 52 visits. If the patient does not agree to a site visit, they will be contacted by telephone to inquire about safety status.
- b All patients will have a phone call Follow-up Visit 2 weeks after the last dose of the IMP to collect safety information.

- c Height to be measured only at Screening.
  - d Vital sign measurements (sitting BP, heart rate, temperature, and respiratory rate): 3 separate seated BP and heart rate measurements should be taken with at least 1 minute between readings, following a 5-minute rest period and prior to phlebotomy (see Appendix C).
  - e Patients will measure their fasting glucose levels via SMBG and discuss results with site personnel at clinic or phone visits, or **unscheduled** phone contacts. The SMBG measurements obtained with glucose meters are displayed as plasma glucose concentration. From randomization through Week 18, glimepiride or glimepiride-matching placebo dose adjustments will be made based on algorithm provided in protocol.  

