### **9.1.5.4 Blood pressure measurements**

Systolic BP and DBP will be assessed at all on-site visits. Blood pressure measurements taken as described in Section 9.2.1.4 with details provided in Appendix C.

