### **Observation period of safety endpoints**

The observation period of safety data will be divided into 3 segments:

- The pre-Treatment Period is defined as the time between the date of informed consent and the first dose of double-blind IMP.
- The on-Treatment Period (TEAE period) is defined as the time from the first dose of double-blind IMP up to 10 days (1 day for hypoglycemia) after the last dose of double-blind IMP, regardless of the introduction of rescue therapy. The 10-day interval is chosen based on the half-life of the IMP (approximately 5 times the half-life of sotagliflozin) in patients with moderate renal dysfunction.
- The post-Treatment Period is defined as the time starting 11 days after the last dose of double-blind IMP (the on-Treatment Period).

The baseline value for safety endpoints in the safety population is the last available value (or the average of all values for creatinine or eGFR) prior to the first administration of the double-blind IMP.

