#### 10.1.1.1.1 On-site Visit 1 (Week -4) Screening Visit

The following procedures/assessments will be performed at Visit 1 (Week -4):

- Obtain the informed consent:
  - The patient will receive verbal information concerning the aims and methods of the study, its constraints and risks and the study duration. Written information will be provided to the patient. Written informed consent must be given by the patient and Investigator prior to any investigations.
  - [REDACTED]
  - [REDACTED]
- Complete physical examination including height, body weight, and vital signs (SBP and DBP, HR, and respiratory rate). After 5 minutes resting, seated SBP, DBP, and HR will be assessed 3 times with at least 1 minute between each measurement (see Appendix C for details).
- IRT to be notified (allocation of identification, registration of screening).
- Assessment of all inclusion/exclusion criteria.
- Collection of demographic data (age, gender, and ethnic origin).
- Assessment of the patient's medical and surgical history: to include history of T2D, treatment and complications (eye, kidney, amputations, etc); history of smoking/tobacco use; history of alcohol and drug abuse.
- Patient diary is dispensed and instructions/training are provided.
- Concomitant medication and medication history, including any prior medications for T2D.
- 12-lead ECG.
- The following laboratory testing (by the central laboratory):
  - FPG

- HbA1c
- Serum pregnancy testing for WOCBP or serum FSH and estradiol (for women of nonreproductive potential if definition of postmenopausal or premenopausal cannot be satisfied; see Appendix A)
- Clinical chemistry (including amylase, lipase) and hematology
- Fasting lipids
- Urinalysis (dipstick and microscopy)
- AEs/SAEs/AESI/EOSI and hypoglycemia (if any) are reported.
- Patients are instructed to return to the site in fasting status for Visit 2 (Week -2).

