### **Measurement Technique**

[figure not shown]
At visit 1, immediately following arm selection, with the patient in the same position, an additional seated BP should be measured in the selected arm (at least 1 minute after last measurement).

At all other on-site visits, following the 5-minute rest period, 3 separate seated BPs should be measured in the arm selected at Visit 1, with at least 1 minute between BP measurements and with the cuff fully deflated between measurements.

All 3 BPs will be recorded in the patient's e-CRF. The mean of the 3 seated BPs will constitute the BP value for that visit.

Three seated pulse rate measurements will be obtained. The mean of the 3 seated pulse rate measurements will constitute the pulse rate value for that visit.

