2 STATISTICAL AND ANALYTICAL PROCEDURES

2.1 ANALYSIS ENDPOINTS

2.1.1 Demographic and baseline characteristics

The baseline value (with the exception of serum creatinine and eGFR) is defined generally as the last available value before the first dose of double-blind IMP or the last available value prior to randomization for patients who were randomized but never exposed to IMP.

For serum creatinine and eGFR, the baseline value is defined as the average of all values before the first dose of double-blind IMP for those randomized and exposed or before randomization for those who were randomized but never exposed to IMP.

All baseline safety and efficacy parameters are presented along with the summary statistics in the safety and efficacy sections ([Section 2.4.5](#) and [Section 2.4.4](#)).

Demographic characteristics

Demographic characteristics to be summarized are:

- Age (years) derived as: (Year of informed consent - Year of birth).
- Age categories (<50, ≥50 to <65, ≥65 to <75, ≥75 years).
- Gender (Male, Female).
- Race (White, Black or African American, Asian, American Indian or Alaska native, Native Hawaiian or other pacific islander, Multiple, Unknown).
- Ethnicity (Hispanic or Latino, Not Hispanic or Latino, Unknown).
- HbA1c (%) at screening visit.
- Randomization strata of HbA1c (≤8.5%, >8.5%) at screening visit (based on IRT data).
- SBP at screening visit.
- Randomization strata of SBP (<130 mmHg, ≥130 mmHg) at screening visit (based on IRT data).
- Baseline body mass index (BMI) (kg/m²) derived as: (Weight in kg)/(Height in meters)².
- Baseline BMI categories (<30, ≥30 kg/m²).
- Country.

Disease characteristics at screening or baseline

Disease history includes:

- Duration of diabetes (years) derived as: (Date of informed consent - Date of diagnosis of diabetes + 1)/365.25.
- Duration of diabetes categories (<10, ≥10 years).
- Age at diagnosis of diabetes (years) derived as: Year of diagnosis of diabetes - Year of birth.
- Duration of metformin treatment (years): (date of informed consent - date of first intake of metformin + 1)/365.25.
- Daily dose of metformin (mg) at baseline.
- Categorized daily dose of metformin at baseline (<1500, ≥1500 to <2500, ≥2500 mg).
- Baseline diabetic microvascular complications (Yes, No) (ie, diabetic retinopathy, diabetic neuropathy, diabetic peripheral neuropathy [sensory or motor], diabetic autonomic neuropathy, diabetic nephropathy, and diabetic foot infection).
- eGFR at screening (mL/min/1.73 m²).

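### The Week 12 SBP ANCOVAs use one of three pre-treatment SBP visits as a continuous covariate, and so give up some precision, most of all in the two SBP ≥130 mmHg tests

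*SAP*

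**What the plan says.** **Collection.** Protocol 9.1.5.4: "Systolic BP and DBP will be assessed at all on-site visits". The flow chart (Protocol 1.2) schedules vital signs at Visit 1 (Week -4), Visit 2 (Week -2) and Visit 3 (Day 1), and its footnote says "3 separate seated BP and heart rate measurements should be taken with at least 1 minute between readings". Appendix C to the protocol adds: "The mean of the 3 seated BPs will constitute the BP value for that visit". At Visit 1 the sequence differs. Both arms are measured twice to choose the arm with the higher SBP, then "an additional seated BP should be measured in the selected arm". That still leaves three readings in the chosen arm.

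**Baseline.** SAP 2.1.1 defines it, except for serum creatinine and eGFR, as the "last available value before the first dose of double-blind IMP or the last available value prior to randomization" (the second part applies to patients never dosed). For SBP this is normally Visit 3. For creatinine and eGFR, all pre-dose values are averaged.

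**Model.** SAP 2.4.4.2 fits treatment, the Screening HbA1c stratum, the Screening SBP stratum (<130, ≥130 mmHg) and country, "and the corresponding baseline secondary endpoint value as a covariate". It then removes the SBP stratum for the analyses in patients with baseline SBP ≥130 mmHg. Protocol 11.4.2.2 has the same single baseline covariate but does not mention that removal.

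**Testing.** SAP 2.4.4.4 lists 12 ordered hypotheses. Week 12 SBP occupies steps 3 (≥130 mmHg) and 4 (all patients) against glimepiride, and steps 9 and 10 against placebo.

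**The concern.** A single visit's SBP is a noisy measure of a patient's usual level, so as a covariate it removes only part of the between-patient variance at Week 12. Two further triplicate values are already in the database. Visit 2 SBP enters no model, and Visit 1 SBP enters only as a two-level stratum in the all-patient tests.

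Step 3 is the point of interest. It is run in the smaller subset, its model carries no earlier SBP, and a miss there stops steps 4 to 12, among them both placebo-controlled HbA1c comparisons. The sample size sections give power for HbA1c only, so the plan does not show how much margin step 3 has.

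**Working it through.** **1. The plan's own figures.** These concern HbA1c only. Normal approximation, power = Φ(Δ/SE − 1.96):

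- Non-inferiority, 310 per arm: SE = 1.1·√(2/310) = 0.0884; 0.3/0.0884 − 1.96 = 1.44; 92.4% (stated at least 90%).
- Completers, 217 per arm after 30% dropout: 81.1% (stated 80%).
- 400 mg versus placebo, 310 and 155, 0.6 and SD 1.2: 99.9% (stated above 99%).
- 200 mg versus placebo, 155 and 155, 0.5 and SD 1.2: 95.6% (stated 95%).

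All reproduce. There is no SBP figure to reproduce.

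**2. Assumptions for SBP.** SD of a visit mean 14 mmHg (variance 196), mean 130 mmHg, normal distribution, common between-visit correlation ρ of 0.5 to 0.7, and either 0 or 25 mmHg² of extra Week 12 variance. None of these is in the documents.

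**3. Subset, planned model (Visit 3 only).** Residual variance as a fraction of the total is 1 − ρ² with one baseline visit. With Visit 3 plus the mean of Visits 1 and 2, it is 1 − 3ρ²/(1 + 2ρ). Selecting on Visit 3 SBP does not change these, because Visit 3 is in the model.

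| ρ | Visit 3 only | plus Visit 1/2 mean | reduction | reduction with 25 mmHg² added |
|---|---|---|---|---|
| 0.5 | 0.750 × 196 = 147.0 | 0.625 × 196 = 122.5 | 16.7% | 172.0 to 147.5: 14.2% |
| 0.6 | 0.640 × 196 = 125.4 | 0.509 × 196 = 99.8 | 20.5% | 150.4 to 124.8: 17.0% |
| 0.7 | 0.510 × 196 = 100.0 | 0.388 × 196 = 76.0 | 24.0% | 125.0 to 101.0: 19.2% |

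The range is 14 to 24%. Since 1/(1 − 0.142) = 1.17 and 1/(1 − 0.24) = 1.32, that is worth 17 to 32% more patients.

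**4. All patients, planned model (Visit 3 plus stratum).** By simulation under the same assumptions:

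| ρ | planned residual SD | with Visit 1/2 mean | reduction | reduction with 25 mmHg² added |
|---|---|---|---|---|
| 0.5 | 11.74 | 11.07 | 11% | 9.4% |
| 0.6 | 10.78 | 9.99 | 14% | 11.6% |
| 0.7 | 9.59 | 8.72 | 17% | 13.7% |

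A run with mean 132 mmHg and variance 200 gave 17.5% at ρ = 0.7, so the range is about 9 to 18%. At ρ = 0.6 the residual SD without the stratum would be 11.21. The stratum therefore already recovers (11.21² − 10.78²)/(11.21² − 9.99²), or about 36%, of the available gain; across all the patterns tried, 24 to 38%.

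**5. Decaying correlation.** Three assumed patterns, without the extra 25 mmHg²:

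| correlation with Week 12 (Visits 3, 2, 1) | adjacent pre-treatment visits; Visit 1 with Visit 3 | all patients | subset |
|---|---|---|---|
| 0.60, 0.56, 0.53 | 0.70; 0.65 | 5% | 8% |
| 0.55, 0.50, 0.46 | 0.65; 0.60 | 4% | 6% |
| 0.60, 0.55, 0.50 | 0.75; 0.70 | 3% | 4% |

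**6. What it does to power.** Assume half the patients have SBP ≥130 mmHg, so step 3 compares 155 with 155 and step 9 compares 155 with 77.5. At ρ = 0.6 the subset residual SD goes from 11.2 to 10.0.

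- True difference 4 mmHg: step 3 from 88.1% to 94.1%; step 9 from 72.7% to 82.1%.
- True difference 4 mmHg, first decaying pattern: step 3 from 88.1% to 90.5%; step 9 from 72.7% to 76.2%.
- True difference 5 mmHg: step 3 is already at 97.5% as planned. At 6 mmHg it is above 99%.

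**The case against.** The strongest reply is that nothing is broken. ANCOVA on the last pre-dose value is unbiased and holds its Type I error rate, so this is a preference about efficiency. That stands.

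The size is also open to challenge. Equal correlation supposes that Week -4 predicts Week 12 as well as Day 1 does, and the protocol gives reasons for doubt:

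- Visit 1 readings come out of the arm-selection procedure.
- Diet and exercise instruction starts at Visit 2.
- Protocol 8.8.1 asks for constant antihypertensive doses only for the 12 weeks after randomization.

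This stands too, and it is why the decaying patterns must be reported beside the others. It does not count against the method: a separate covariate lets the regression set its own weight, which averaging the visits into baseline would not.

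The gatekeeping argument weakens at large effects. Protocol 4.2 cites a Phase 2 SBP reduction of 10 to 15 mmHg in patients at or above 130 mmHg, not stated to be placebo-corrected. At a between-group effect near that, step 3 hardly needs help.

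A reader might infer that all four tests adjust for the last value alone. The documents do not support that, because the all-patient models retain the Screening SBP stratum. A reader might also take the averaged creatinine and eGFR baselines as showing that SBP was overlooked. They do not: SAP 1.5 attributes that averaging to a CDISC user guide for diabetic kidney disease, not to a precision rule. It shows only that a multi-visit baseline is workable in this trial.

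**Conclusion.** The point holds as a modest efficiency gain, not as an error. The planned SBP models are valid but leave collected pre-randomization information unused: all of it in the two ≥130 mmHg tests, and most of it in the two all-patient tests.

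Under equal between-visit correlation of 0.5 to 0.7, the recoverable residual variance is about 14 to 24% in the subset and 9 to 18% in all patients. Under decaying correlation it is about 3 to 8%. Every one of these figures rests on assumed correlations. The gain was positive in every pattern tried.

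It could matter for passing step 3 if the true subset difference is around 3 to 4 mmHg. Near the Phase 2 figure it would mainly narrow the intervals. The documents do not support saying that the sequence is at risk, because they state no SBP effect or variance.

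**What to change.** Keep the endpoint, the baseline definition, the ≥130 mmHg subset and the strata as they are. In the four Week 12 SBP ANCOVAs, add the mean of the Visit 1 and Visit 2 SBP values as a second continuous covariate. If one of the two is missing, use the other.

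State whether the new term also enters the imputation model. SAP 2.4.4.1 imputes from the strata and the corresponding baseline, and allows the retrieved-dropout model with as few as five such patients per arm. The simple choice is to leave that sparse model alone and accept a slightly smaller gain for patients with imputed values.

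Timing decides the status of the analysis. SAP version 3 is dated 03-Apr-2020, after the database lock of 12Sep2019, and no unblinding date is given. Make this the tested model only if the blind is documented as intact, and record the departure from Protocol 11.4.2.2. Otherwise report it as a labelled supplementary SBP analysis beside the planned one.

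The cost is one model term, one degree of freedom and a sentence on imputation. No new data are needed.
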